8.3 Population for Analysis

The following populations will be considered for the analyses:

- Intention to treat (ITT) population: All randomized participants, regardless of protocol adherence. The primary endpoint analysis will be performed on all subjects on an intention-to-treat basis.
- Per-protocol population (PP): Includes all subjects who have undergone the treatment for which they were allocated.
- Patients randomized to HAI-treatment or liver transplantation actually receiving these treatments'
- Safety population: Includes all subjects who have received at least one dose of study medication. Subjects who withdraw from the study will be included in the safety analysis. A list of withdrawn subjects, preferably with the reasons for withdrawal, will be made.
- Subgroups defined by: Left versus right sided primary tumour, degree of PET uptake in liver, FONG/Oslo-score

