5.1.4.5 Pump removal

In the case of progressive disease or any other reason where use of pump/catheter in HAI group becomes obsolete and is not acceptable to the patient, the pump may be removed (at OUH, dept of GI surgery, HPB-section) through a local incision. The catheter will be ligated and left in situ. In the case of liver resection the catheter may be removed (with the pump) or left in situ, at the surgeon's discretion. During longer drug-free periods, a glycerol solution will be added in the pump chamber to prevent thrombosis of the catheter until the next treatment cycle. Post-resectional use of HAI will be off protocol.

5.1.4.6 Dosage of FUDR, Dexamethasone (Dex), proton pump inhibitors and pump administration.

All patients start HAIP chemotherapy 4 to 8 weeks after surgery, after confirmation of bilobar hepatic perfusion and lack of extrahepatic perfusion.

The pump reservoir is filled percutaneously with 0.12 mg/kg floxuridine together with 35,000U of heparin, 25 mg of dexamethasone and enough normal saline for a total volume of 35cc. Both are to be delivered as a 14-day continuous infusion through the pump. For patients who are more than 25% above ideal body weight, the actual dose of floxuridine is calculated by using a weight that averages the patient's actual weight and their ideal weight.

Patients will commence treatment at a minimum 2 weeks after pump placement. Therapy will be administered in a 4-week cycle. HAI therapy starts on day 1 of each cycle, and the pump will be emptied and filled with heparin (35,000 units) and normal saline on day 15. Systemic chemotherapy will be administered on day 2 and day 16 of each cycle.

Until completion of HAI chemotherapy, patients will receive prophylactic proton pump inhibitor 20mg once daily.

To assess early side effects and toxic reactions, patients will be hospitalized at the Gastrointestinal ward at Rikshospitalet for 24 hours following start of first FUDR administration. At later occasions, the treatment will be offered as an outpatient procedure.

5.1.4.7 Drug Information floxuridine.

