 - Monthly pregnancy testing should be performed in women of childbearing potential (WOCBP) as long as they receive chemotherapy according to study protocol. This can be done with a urine test at home combined with contact with the study team by phone
 - A calendar for oncologist visits and provision of systemic chemotherapy is created by coordinating nurse. Control scans are ordered for each 2nd month for the first year following randomization and as long as the patients receive chemotherapy, each 3rd month for the second year and each 6th month for the third year. MDT meetings are scheduled for one week following each new scanning to assess response and possible resectability
 - Out-patient control appointments are scheduled for outcome assessment including QoL-scoring (3, 6, 9, 15, 18, 21 and 24 months)
- Patients in HAI group (group 2 a and 2b)
 - A calendar of reservoir refills is created and harmonized with provision of systemic treatment.
 - A laparotomy is performed within 2 weeks from randomization with insertion of catheter and reservoir for HAI-pump.
- Patients in transplant group
 - Oncologists are instructed to avoid Avastin in systemic chemotherapy while the patient is listed.

Table 3: Overview of screening procedures, End of study/Withdrawal

Overview of screening procedures, End of study Withdrawal												
Item	ICF	Inc/Ex	Med Hist	Prior Trea	Phys Exam	Vit Sign	ECOG	CT/ MR	QoL	Blood Sample	Adverse Event	Survival Assessment
Screening	x	x	x	x	x	x	x	x	x	x	x	
EOS/Withdrawal											x	x

Table 4: Calendar of cycles and events for patients in HAI group

Calendar of cycles and events for patients in HAI group								
Day cycle 1 + 2	1	2	15	16	29	30	44	
Day cycle 3 + 4	61	62	75	76	89	90	104	
Pump refill FUDR at OUS	x				x			
Pump refill HepNaCl at OUS			x					x
Systemic chemo local hospital		x		x		x		

Table 5: Calendar of cycles and events for patients in control group and on waiting list for LTx-group

Calendar of cycles and events for patients in control group and on waiting list for LTx- group							
Day cycle 1 + 2	1		15		29		44
Day cycle 3 + 4	61		75		89		104
Systemic chemo local hospital	x		x		x		x

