8.5 Statistical Analysis

8.5.1 Primary analysis

- Primary variable: Overall survival at 2 years from randomization
- Assessment: From the electronic medical records (EPJ)
- Metric: Hazard ratio
- When the last recruited patient has reached two years follow-up or censor.

The primary analysis will be done by Cox regression with treatment group as covariate, adjusted for stratification factors in the randomization.

Primary population: By intention-to-treat (ITT), i.e. all randomized patients regardless of protocol adherence.

The treatment effect will be presented as hazard ratios between the two treatment groups and the standard of care group, in addition to 95% confidence intervals.

The null hypothesis to be tested is that there is no difference between the treatment groups on overall survival after 2 year. If the null hypothesis is rejected on a 5% significance level, the pairwise treatment group's differences will be tested on the 5% level with the family-wise error rate sustained by the closed test principle.

There will be no handling of missing values. All patients will be followed-up until 2 years or death of any reason. Patients lost to follow-up will be censored at time of last observation, and handled accordingly.

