8.5.2 Secondary analyses

- Per-protocol comparison of overall survival at 2 years
- ITT liver-progression-free survival,
- Rates of liver resection in HAI group compared with control group and with transplantation rate for TX group. Standard approximation to binary outcomes with Fisher exact test or chi-square.
- Quality-of-life as measured by EORTC-30

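### The per-protocol comparison of 2-year survival counts from randomisation but admits only patients who lived to receive their treatment, which biases it toward HAI slightly and toward transplant potentially a lot

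*Protocol*

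**What the plan says.** Section 8.3 defines the per-protocol set by what happened after allocation: "Includes all subjects who have undergone the treatment for which they were allocated". It lists a further set in the same terms: "Patients randomized to HAI-treatment or liver transplantation actually receiving these treatments". Section 8.5.2 includes among the secondary analyses a "Per-protocol comparison of overall survival at 2 years". It gives no model, landmark or separate time origin. The origin stated in Table 1 and section 8.5.1 is randomisation: "Primary variable: Overall survival at 2 years from randomization".

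The route to treatment differs by arm.

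- **HAI.** Section 5.5: "A laparotomy is performed within 2 weeks from randomization with insertion of catheter and reservoir for HAI-pump". Section 5.1.4.6 then gives two intervals to the first floxuridine dose: "All patients start HAIP chemotherapy 4 to 8 weeks after surgery" and "Patients will commence treatment at a minimum 2 weeks after pump placement".
- **Transplant.** Section 5.1.2 requires acceptance by the MDT and listing for an extended-criteria organ. No waiting time or limit is given. Section 3 foresees removal from the list, and Table 7 (section 5.6.5) sends patients with extrahepatic disease or lymph-node metastasis to palliative treatment.
- **Control.** Section 5.5 allows second-line chemotherapy to have begun before randomisation, and no waiting step is described.

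For the primary endpoint, section 8.3 says: "The primary endpoint analysis will be performed on all subjects on an intention-to-treat basis".

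**The concern.** Membership of the per-protocol set is settled after the survival clock has started. To be counted as treated, a patient allocated to HAI or transplant must survive until treatment, so the time between randomisation and treatment is free of deaths by construction. This is immortal-time bias. Control patients face almost no such hurdle, so their early deaths are counted in full.

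A comparison built this way moves toward both experimental arms even when neither treatment works. The longer the wait, the larger the shift. With 9 transplant patients planned (section 8.1), losing two early deaths would visibly change the result, and readers of an open-label trial may take the per-protocol figure as the effect of actually being transplanted.

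**Working it through.** **The plan's own figures.** The protocol gives no figure for the per-protocol analysis. Its sample size, which supplies the 30% used here, can be reproduced: with unpooled variances, n = (1.96 + 0.842)² × (0.30×0.70 + 0.75×0.25) / 0.45² = 15.4, hence 16 per group as in section 8.1.

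**Inputs.**
- Control 2-year survival of 30% and planned groups of 18, 18 and 9 (section 8.1).
- HAI delay of 2 to 10 weeks. The upper end is 2 weeks to laparotomy plus 8 weeks to the first dose. The lower end covers receipt counted at pump placement, or the shorter start interval.
- Transplant wait: not stated, so assumed to be 3, 6, 9 or 12 months.
- Assumptions: exponential survival, no treatment effect in any arm, no delay for controls, follow-up cut at 24 months.

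**Formulas.** The hazard is λ = −ln(0.30)/24 = 0.0502 per month. A fixed delay d keeps a fraction S(d) = exp(−λd) of the arm. Per-protocol 2-year survival is then 0.30/S(d). At 10 weeks (2.30 months), S = 0.891 and 0.30/0.891 = 33.7%. At 6 months, S = 0.740 and 0.30/0.740 = 40.5%. Hazard ratios come from Cox models on 400,000 simulated patients per arm.

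| Arm, fixed delay | Kept | Per-protocol 2-year OS (truth 30%) | HR (truth 1) |
|---|---|---|---|
| HAI, 2 weeks | 98% | 30.7% | 0.97 |
| HAI, 4 weeks | 95% | 31.4% | 0.93 |
| HAI, 10 weeks | 89% | 33.7% | 0.85 |
| Transplant, 3 months | 86% | 34.9% | 0.81 |
| Transplant, 6 months | 74% | 40.5% | 0.65 |
| Transplant, 9 months | 64% | 47.1% | 0.52 |
| Transplant, 12 months | 55% | 54.8% | 0.41 |

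**Hand check at 6 months.** Deaths per patient kept are 1 − 0.405 = 0.595. Person-time is 6 + 0.595/0.0502 = 17.9 months. The rate is 0.595/17.9 = 0.0333, and 0.0333/0.0502 = 0.66, close to the Cox value.

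**Variable waits.** With exponentially distributed waits of mean 3, 6, 9 and 12 months, the transplant hazard ratio is 0.83, 0.72, 0.65 and 0.59.

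**Other control survival.** Section 1.4 gives 10 to 12 months from the start of second-line treatment. Read as a median of 12 months, true 2-year survival is 25%; the per-protocol figure becomes 28.6% for HAI at 10 weeks, and 35.4% and 50% for transplant at 6 and 12 months.

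**Patients lost.** HAI: 18 × 0.023 = 0.4 to 18 × 0.11 = 2.0. Transplant at 6 months: 9 × 0.26 = 2.3.

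**False positives at trial size (6,000 simulated trials per scenario).** In favour of HAI, 18 against 18: 2.6% without delay, 5.2% at 10 weeks. In favour of transplant, 9 against 18: 1.7% without delay, 4.4% at 6 months, 7.1% at 12 months.

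**Cause confirmed.** Restricting both arms to patients alive at the same time d and comparing them from there returns hazard ratios of 0.995 to 1.002 in every scenario.

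**The case against.** The strongest reply is that this is one supportive line in section 8.5.2, beside an intention-to-treat primary analysis that it cannot touch. Section 8.4 leaves further detail to a SAP, which could add a landmark without contradicting the protocol. That limits the weight of the point but does not remove it: section 8.3 already fixes who is in the set, and a SAP that applied this definition from randomisation would reproduce the bias.

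Several stronger readings are tempting, and the protocol does not support them.

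- *Progressors in general are removed from the experimental arms.* Section 5.6.3 keeps a transplant patient with progression on the list while chemotherapy is changed. In the HAI arm, progression stops the pump once it is in use, and such a patient has already received HAI. Only extrahepatic or nodal spread diverts transplant patients (Table 7). That diversion probably adds selection in the same direction, but it is not quantified here.
- *The analysis would show benefit even if neither treatment worked.* This holds on average only. At this sample size, a significant false result in favour remains uncommon.
- *Both arms are equally affected.* The HAI shift is small across its whole range.
- *The set of patients actually receiving HAI or transplant is also compared with control.* No analysis in section 8.5.2 uses it, and Table 1 asks only for the number of HAI patients treated.
- *Being listed first makes this the leading secondary analysis.* Section 8.5.2 states no hierarchy, and Table 1 does not list per-protocol survival as an endpoint.

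It is also fair that the large transplant figures rest on an assumed wait, and that variable waits give milder ones.

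**Conclusion.** The point stands as a weakness of a secondary analysis. As written, the per-protocol comparison of 2-year survival is biased on average toward both interventions. For HAI the distortion is a few percentage points at most over a 2 to 10 week delay. For transplant it could be large, but its size cannot be fixed from the protocol because no waiting time is given. The figures assume exponential survival and no treatment effect, and count only deaths before treatment. Inference from the primary intention-to-treat analysis is unaffected.

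**What to change.** 1. Define receipt of treatment for each arm; for HAI, say whether it means pump placement or the first floxuridine dose.
2. Replace the per-protocol survival comparison from randomisation with one or both of the following. (a) A landmark analysis at one common time in all arms (for example 3 and 6 months), including only patients alive then, classified by treatment received by then, with survival counted from that point. (b) A Cox model from randomisation with receipt of HAI or transplant as a time-dependent covariate.
3. Report any unadjusted per-protocol or as-received survival as descriptive, with intention-to-treat as the basis for inference.
4. The sponsor must reconcile the two HAI start intervals in section 5.1.4.6.

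The cost is a wording change and modest programming. Section 7.2 already requires treatments, and the time points of treatment changes, to be in the source records. The statistical price is low precision with about 9 transplant patients, fewer still at a landmark. Neither method removes selection by prognosis among those who reach treatment, so the results need cautious wording. The change should be made before outcomes are analysed, since the trial is open label.

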2 STUDY OBJECTIVES AND RELATED ENDPOINTS

The objectives and endpoints of the study are listed in Table 1 below. The primary endpoint is Overall survival at 2 years after randomization. Safety and toxicity grade 3-5 toxicity will be reported.

Table 1 Objectives and related endpoint:

Objectives	Endpoints	Assessment
Primary: Overall survival	Overall survival at 2 years after randomization	Medical records
Secondary: 1. Efficacy	Overall survival (OS), at 5- and 10-years after randomization.	Medical records
Radiological response to treatment	Response rate	CT/MRI-scans RECIST 1.1
2. Efficacy	Resection rate	Medical records
3. Efficacy	Number of patients randomized til HAI receiving HAI-treatment	
4. Efficacy	Quality of life	EORTC QoL C30
Safety all patients	Adverse events in patients receiving chemotherapy	NCI-CTC 5.0 grade III-V toxicity
Safety in patients receiving resection/transplantation.	Major surgical complications	Accordion Grade III - VI
Exploratory	Molecular analyses related to disease-free and overall survival	Biobank stored blood and tumour tissue
	Progression free survival (PFS). (PFS will be calculated both with and without sensing patients receiving resection or transplantation at time of resection/transplantation) Disease free survival after liver resection/transplantation in the different treatment arms	CT/MRI-scans RECIST 1.1

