5 TREATMENT

For this study the drugs that are used for HAI are fluorodeoxyuridine also known as floxuridine (FUDR, Fresenius Kabi, LLC, USA) and dexamethasone. These drugs are defined as Investigational Medicinal Product (IMP). The patients will receive 20 mg proton pump inhibitor.

All patients will receive second line standard systemic chemotherapy at the discretion of the treating medical oncologist. Resection in the HAI and standard care groups will be undertaken only provided sufficient response on 2nd line chemotherapy (with or without HAI/FUDR) has been achieved (defined as ≥ 10 % response on median diameter of two target lesions, i.e. measured as with RECIST 1.1. but with a trial-specific cut-off). The study is a three- armed study, where the control arm receives systemic 2nd line chemotherapy only, one arm receive systemic chemotherapy and HAI and the third arm 2nd line systemic chemotherapy and liver transplantation.

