5.1.4.11 Expected complications related to the HAI pump

Surgical complications related to HAI pump placement may occur. A retrospective review of 544 HAI pump placements was performed at MSKCC.(19) Pump placement was typically combined with a partial liver resection. A simultaneous partial colectomy was performed in 136 patients (25%). No mortality attributed to the pump was reported. The most common complications were unrelated to the pump: wound infection of the laparotomy wound, atelectasis, prolonged ileus, and intra-abdominal abscess. Pump related morbidity (including dysfunction) occurred in 120 patients (22%). HAIP chemotherapy with floxuridine was impossible or discontinued in only 9% of patients. In 9 patients (2%) extrahepatic perfusion was found postoperatively, which could be resolved in 7 patients. In 9 patients (2%) postoperative technetium scan showed incomplete liver perfusion. Most common explanation was a non-ligated accessory or replaced hepatic artery, which was resolved with embolization or surgical ligation. Cross-over flow developed instantly or could be confirmed after four weeks. Hepatic arterial thrombosis can occur immediately after surgery (13 patients, 2%), of which a third could be salvaged with anti-coagulation. Thrombosis also occurred in 11 patients (2%) as a late complication resulting from HAIP chemotherapy. However, in the second half of the study only one patient developed a hepatic arterial thrombosis. The higher incidence in the first half was attributed to the intra-arterial administration of mitomycin C. Pump pocket infection was found in 24 patients (4%) and could be salvaged with parenteral antibiotics in half of these patients. In some patients with pump site infection, replacement and repositioning of the pump may be necessary. Simultaneous partial colectomy did not increase the rate of pump pocket infection. Arterial haemorrhage occurred in only 1 patient. The incidence of biliary sclerosis due to HAIP chemotherapy in a retrospective analysis of 293 patients was 5.5%. Risk factors most significantly associated with biliary sclerosis were dose, number of cycles, abnormal nuclear medicine scan, and postoperative infections. All patients were managed successfully with biliary stenting and/or dilatation.(28)

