6.2.3 Duration Period for Reporting AE and SAE

Any new primary cancer (non-related to the cancer under study) should be recorded in the CRF.

For each patient the standard time period for collecting and recording of AE and SAEs in the CRF (reporting of SAE to sponsor) will begin at start of study treatment and will continue for at least 30 days following the last dose of study treatment for each patient in patients receiving FUDR.

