6.5 Data Monitoring Committee (DMC)

In case of death occurs in the HIA/FUDR arm, the independent Data Monitoring Committee (DMC) will recommend whether to continue, modify or terminate the trial.

The DMC will consist of two independent liver surgeons, [name] and [name] who both are employed at hospitals outside of Oslo University Hospital.

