8.5.3 Safety analyses

The adverse events will be presented descriptively by means of frequency and percentages to evaluate both the rate of incidence and event occurrence among the different treatment groups. The descriptive tables will be presented with respect to intensity, seriousness and relationship to the treatment.

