10 RISK VERSUS BENEFIT ASSESSMENT

It is the firm view of the investigators that the potential side-effects of the two interventions in question are more than outweighed by their potential benefit and by the reduced side effects from a sparing effect on standard systemic chemotherapy.

This is a randomized trial where the control arm receives standard systemic chemotherapy. The overall prognosis for this selected group of patients is very poor and 2nd line chemotherapy comes with a range of side effects that are (to a variable extent) tolerated as (today) no other treatment alternative exist. Irinotecan and Oxaliplatin may induce liver toxicity to an extent completely precluding liver surgery.

From the available literature, patients receiving additional intra-arterial chemotherapy (HAI) may expect a better response and greater possibility of reaching surgery (liver resection) and improved overall survival. Patients receiving liver transplant can expect a significantly improved survival compared to standard chemotherapy alone. The hypothesis is that the experimental treatments are better than today's standard treatment and thus more patients will reach resectional surgery in the trial and henceforth in non-trial settings in the future.

The insertion of HAI pump is an operative intervention with marginal operational risk. Apart from a 1-2 % risk of wound dehiscence, there are no significant risks from the surgery as such. General anaesthesia risk is considered negligible. HAI (FUdR) may cause biliary toxicity. These findings have previously been published and are well known as the drugs have been in clinical use for more than 10-years in the US. The well-documented risk of bile duct inflammation resulting from HAI has been significantly reduced with the use of steroids and dose reduction in the event of increasing LFTs. As HAI is assumed to reduce the dosage and cycles necessary of systemic chemotherapy, we believe that the side effects/complications of the two regimens may well be balanced even with a laparotomy only in the intervention groups.

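### The adverse-event window, safety set and DMC trigger rest on undefined drug dosing or on the HAI arm alone, and conflict with the protocol's all-arm safety rules, so some pump-operation and transplant harms could be missed.

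*Protocol*

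**What the plan says.** All references are to the protocol.

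- **Collection window (6.2.3).** Recording of AEs and SAEs "will begin at start of study treatment and will continue for at least 30 days following the last dose of study treatment". The end is stated only for patients receiving FUDR, and *study treatment* is not defined.
- **What is recorded.** Section 6.2.1 names only events related to systemic chemotherapy or to FUDR pump administration. Section 6.2.4 asks for all adverse events whatever the arm, section 6.3.1 extends SAE reporting to patients without HAI, and section 6.4 covers all AEs and SAEs during the trial.
- **Safety set (8.3).** "Safety population: Includes all subjects who have received at least one dose of study medication". *Study medication* is not defined. Section 5 designates only floxuridine and dexamethasone as the investigational product, and says that all patients receive second-line systemic chemotherapy.
- **Safety analysis (8.5.3).** Adverse events are tabulated "to evaluate both the rate of incidence and event occurrence among the different treatment groups".
- **Surgical endpoint.** The Table 1 row is "Safety in patients receiving resection/transplantation", graded Accordion III to VI. Section 5.10 records surgical complications of grade 3 to 6 without naming a procedure.
- **DMC (6.5).** "In case of death occurs in the HIA/FUDR arm, the independent Data Monitoring Committee (DMC) will recommend" whether to continue, modify or terminate. No other trigger is given.
- **Operative risk.** Section 10 says of pump insertion: "Apart from a 1-2 % risk of wound dehiscence, there are no significant risks from the surgery as such". Section 5.1.4.11 reports pump-related morbidity, including dysfunction, in 120 of 544 patients (22%).

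**The concern.** Two of the three interventions start with, or consist of, major surgery, but the rules that decide which harms are collected, who is analysed and what reaches the DMC are written around a drug dose or the HAI arm. Other sections are broader, so two people could each follow the protocol and collect different data.

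At stake is the safety side of a risk-benefit judgement made on 18 HAI and 9 transplant patients, where a few uncounted complications would change the picture. An analysis plan can redefine a safety set, but it cannot recover events that were never recorded.

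**Working it through.** The plan states no figure for this point, so the check is a cross-reading plus simple arithmetic.

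**1. Does the pump operation fall inside the window?**
- Laparotomy: within 2 weeks of randomisation (5.5).
- First FUDR: section 5.1.4.6 gives 4 to 8 weeks after surgery, and also a minimum of 2 weeks after pump placement. These conflict and must be reconciled.
- Systemic chemotherapy in the HAI arm: follows the HAI schedule (5.1.1), on day 2 of a cycle whose day 1 is FUDR (5.1.4.6, Table 4).
- Exception: some HAI patients start second-line chemotherapy before the pump (5.1.1).

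For the others, surgery precedes both FUDR and chemotherapy. The gap to the first FUDR dose is at least 14 days on one statement and 28 to 56 days on the other; chemotherapy follows a day later. Taking the first 30 postoperative days as an illustration, a 14-day gap leaves 14 of them outside the window, a 28-day gap 28, and a 56-day gap all 30. This holds whichever drug counts as study treatment. For patients already on chemotherapy, the window may open before surgery if chemotherapy counts.

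**2. Who is in the safety set?** Planned arms are 18 + 18 + 9 = 45 (8.1).
- Study medication = investigational product: at most 18/45 = 40%. The 18 + 9 = 27 control and transplant patients drop out, leaving no groups to compare under 8.5.3.
- Study medication includes systemic chemotherapy: nearly all 45 qualify.

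**3. How many HAI patients could be affected?** Rates come from the series in 5.1.4.11.
- Pump-related morbidity: 120/544 = 22.1%; 18 × 0.2206 = 3.97, about 4 patients.
- HAI impossible or discontinued, 9%: 18 × 0.09 = 1.62 patients; P(at least one) = 1 − 0.91^18 = 0.82.

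Both are upper bounds. The 22% includes device dysfunction, and the section also describes late events that arise after dosing. The 9% includes patients who stopped after receiving FUDR.

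**4. What reaches the DMC?** Planned two-year survival is 75% for HAI and 90% for transplant (8.1).
- HAI: 18 × 0.25 = 4.5 deaths expected; P(at least one) = 1 − 0.75^18 = 0.994.
- Transplant: 9 × 0.10 = 0.9 deaths expected; P(at least one) = 1 − 0.90^9 = 0.61, with no stated trigger.
- Deaths after resection: covered in the HAI arm, not in the control arm.

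**5. Section 10 against the protocol's own data.** Section 5.1.4.11 lists pump pocket infection in 24/544 (4%) and hepatic arterial thrombosis immediately after surgery in 13/544 (2%). Section 1.6 reports 2 of 20 Dutch patients with grade III complications needing reoperation. None of this agrees with a statement that wound dehiscence is the only significant surgical risk.

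**The case against.** A reader might infer that pump-surgery and transplant harms are left out altogether. The documents do not support that. Major complications of transplantation and resection are a Table 1 endpoint. Section 5.10 records grade 3 to 6 surgical complications without limit by procedure, so the pump laparotomy fits. The synopsis lists major complications following surgery, and sections 6.2.4, 6.3.1 and 6.4 reach all arms. A death from the pump operation is a death in the HAI arm and does go to the DMC. Outside the DMC, the sponsor reassesses risk and benefit from SAE reports (6.3.1).

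Nor is it settled that the window always opens after the laparotomy. Section 6.2.3 does not say FUDR; its restriction of the end date to FUDR patients would be redundant if study treatment meant FUDR. Some patients start chemotherapy before the pump. Likewise, section 8.3 does not say investigational product, and the analysis plan may define the safety set.

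The contrast with section 10 also needs care: the 544-patient series typically combined pump placement with liver resection, and section 10 speaks of the surgery itself.

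All of that stands, and it rules out the stronger reading. It does not remove the point. The broader passages contradict sections 6.2.1 and 6.2.3 without overriding them. HAI patients not yet on chemotherapy remain outside the window on either drug definition. Section 5.10 catches only grade 3 to 6. Early arterial thrombosis and pocket infection are operative or device-pocket complications that section 10 omits.

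**Conclusion.** The concern holds as one of inconsistent rules partly tied to drug dosing. Followed as written, sections 6.2.3, 8.3 and 6.5 could miss perioperative harms in an 18-patient arm, reduce the safety set to at most 18 of 45, and send no transplant-arm death to the DMC (0.9 of 9 expected, 61% chance of at least one).

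The harms that could be missed are at most about 4 HAI patients with pump-related morbidity and about 1.6 never dosed, and probably fewer. These sizes assume that the cited series carries over to this trial, that the planned survival rates and arm sizes hold, and, for the window, that study treatment means a drug. If the operation itself were meant, the window would open with it, but section 6.2.3 does not say so and ties its end to a last dose. The conflict between section 10 and section 5.1.4.11 depends on no undefined term.

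**What to change.** - **6.2.1 and 6.2.3:** reconcile with 5.10, 6.2.4, 6.3.1 and 6.4 by opening AE and SAE collection at randomisation in all arms. State when it ends for patients who do not receive FUDR.
- **8.3:** define the safety set as randomised patients who started any protocol intervention (pump laparotomy, second-line chemotherapy or transplantation), presented by arm.
- **Table 1:** add pump placement to the Accordion-graded surgical complications.
- **6.5:** extend DMC notification to deaths in the transplant arm and post-operative deaths in any arm.
- **10:** replace the statement on surgical risk with the figures in 5.1.4.11, noting that the series often included liver resection.
- **5.1.4.6:** reconcile the two statements on when HAI starts; which is intended is for the investigators.

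The cost is protocol wording and a few more CRF entries; the DMC already exists. The HAI safety profile may look slightly less favourable.
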